7.2.1. Summaries of Numeric Laboratory Results

Descriptive statistics will be provided by treatment group for each laboratory test specified in the study protocol as follows:

- Baseline values
- Postbaseline maximum value
- Postbaseline minimum value
- Change and percentage change from baseline to postbaseline maximum value
- Change and percentage change from baseline to postbaseline minimum value

A baseline laboratory value will be defined as the last measurement obtained on or prior to the date/time of first dose of study drug. Change from baseline to a postbaseline visit will be defined as the visit value minus the baseline value. The mean, median, Q1, Q3, minimum, and maximum values will be displayed to the reported number of digits; StD values will be displayed to the reported number of digits plus 1.

In the case of multiple values in an analysis window, data will be selected for analysis as described in Section 3.8.3.

7.2.2. Graded Laboratory Values

CTCAE Version 4.03 will be used to assign toxicity grades (0 to 4) to laboratory results for analysis. Grade 0 includes all values that do not meet the criteria for an abnormality of at least Grade 1. For laboratory tests with criteria for both increased and decreased levels, analyses for each direction (ie, increased, decreased) will be presented separately. Local labs will be graded based on the central lab normal ranges with in-house macro.

7.2.2.1. Treatment-Emergent Laboratory Abnormalities

Treatment-emergent laboratory abnormalities are defined as values that increase at least 1 toxicity grade from baseline at any postbaseline time point, up to and including the date of last dose of study drug plus 30 days for subjects who permanently discontinued study drug. If the relevant baseline laboratory value is missing, any abnormality of at least Grade 1 observed within the time frame specified above will be considered treatment emergent.

7.2.2.2. Summaries of Laboratory Abnormalities

The following summaries (number and percentage of subjects) for treatment-emergent laboratory abnormalities will be provided by lab test and treatment group; subjects will be categorized according to the most severe postbaseline abnormality grade for a given lab test:

- Graded TE laboratory abnormalities
- TE Grade 3 or 4 laboratory abnormalities

For all summaries of laboratory abnormalities, the denominator is the number of subjects with nonmissing postbaseline values up to 30 days after last dosing date.

A by-subject listing of treatment-emergent laboratory abnormalities will be provided by subject ID number and visit in chronological order. This listing will include all test results that were collected throughout the study for the lab test of interest, with all applicable severity grades and abnormal flags displayed.

7.2.3. Liver-related Laboratory Evaluations

Liver-related abnormalities after initial study drug dosing will be examined and summarized using the number and percentage of subjects who were reported to have the following laboratory test values for postbaseline measurements:

- Aspartate aminotransferase (AST): (a) > 3 times of the upper limit of reference range (ULN); (b) > 5 x ULN; (c) > 10 x ULN; (d) > 20 x ULN
- Alanine aminotransferase (ALT): (a) > 3 x ULN; (b) > 5 x ULN; (c) > 10 x ULN; (d) > 20 x ULN

- AST or ALT: (a) > 3 x ULN; (b) > 5 x ULN; (c) > 10 x ULN; (d) > 20 x ULN
- Total bilirubin: > 2 x ULN
- Alkaline phosphatase (ALP) > 1.5 x ULN
- AST or ALT > 3 x ULN and total bilirubin: (a) > 1.5 x ULN; (b) > 2 x ULN

The summary will include data from all postbaseline visits up to 30 days after the last dose of study drug. For individual laboratory tests, subjects will be counted once based on the most severe postbaseline values. For both the composite endpoint of AST or ALT and total bilirubin, subjects will be counted once when the criteria are met at the same postbaseline visit date. The denominator is the number of subjects in the Safety Analysis Set who have nonmissing postbaseline values of all relevant tests at the same postbaseline visit date. A listing of subjects who met at least 1 of the above criteria will be provided.

7.2.4. Shifts Relative to the Baseline Value

Shift tables will be presented by showing change in severity grade from baseline to the worst postbaseline grade up to 30 days after last dosing date. The percentage will be based on subjects with values available at both baseline and postbaseline.

7.3. Body Weight and Vital Signs

Body weight and vital signs are collected at screening and may be collected at unscheduled visits. Thus, only a by-subject listing of vital signs will be provided by subject ID number and time visit in chronological order.

7.4. Prior and Concomitant Medications

Medications collected at screening and during the study will be coded using the current version of the World Health Organization (WHO) Drug dictionary.

7.4.1. Prior Medications

Prior medications are defined as any medications taken before a subject took the first study drug.

Prior medications will be summarized by Anatomical Therapeutic Chemical (ATC) drug class Level 2 and preferred name using the number and percentage of subjects for each treatment group and overall. A subject reporting the same medication more than once will be counted only once when calculating the number and percentage of subjects who received that medication. The summary will be ordered alphabetically by ATC medical class and then by preferred term in order of descending overall frequency within each ATC medical class. For drugs with the same frequency, sorting will be done alphabetically.

For the purposes of analysis, any medication with a start date prior to the first dosing date of study drug will be included in the prior medication summary regardless of when the stop date is. If a partial start date is entered the medication will be considered prior unless the month and year (if day is missing) or year (if day and month are missing) of the start date are after the first

dosing date. Medications with a completely missing start date will be included in the prior medication summary, unless otherwise specified.

Summaries will be based on the Safety Analysis Set. No formal statistical testing is planned.

7.4.2. Concomitant Medications

Concomitant medications are defined as medications taken while a subject took study drug. Use of concomitant medications will be summarized by Anatomical Therapeutic Chemical (ATC) drug class Level 2 and preferred name using the number and percentage of subjects for each treatment group. A subject reporting the same medication more than once will be counted only once when calculating the number and percentage of subjects who received that medication. The summary will be ordered alphabetically by ATC medical class and then by preferred term in descending overall frequency within each ATC medical class. For drugs with the same frequency, sorting will be done alphabetically.

For the purposes of analysis, any medications with a start date prior to or on the first dosing date of study drug and continued to be taken after the first dosing date, or started after the first dosing date but prior to or on the last dosing date of study drug will be considered concomitant medications. Medications started and stopped on the same day as the first dosing date or the last dosing date of study drug will also be considered concomitant. Medications with a stop date prior to the date of first dosing date of study drug or a start date after the last dosing date of study drug will be excluded from the concomitant medication summary. If a partial stop date is entered, any medication with the month and year (if day is missing) or year (if day and month are missing) prior to the date of first study drug administration will be excluded from the concomitant medication summary. If a partial start date is entered, any medication with the month and year (if day is missing) or year (if day and month are missing) after the study drug stop date will be excluded from the concomitant medication summary. Medications with completely missing start and stop dates will be included in the concomitant medication summary, unless otherwise specified.

Summaries will be based on the Safety Analysis Set. No formal statistical testing is planned.

All prior and concomitant medications (other than per-protocol study drugs) will be provided in a by-subject listing sorted by subject ID number and administration date in chronological order.

7.5. Electrocardiogram Results

Electrocardiogram (ECG) analysis results are intended to identify meaningful changes in the QT interval. If potential abnormalities of interest are identified, further analyses may be conducted. Summaries of investigator assessment of ECG readings and ECG data will be provided for the Safety Analysis Set. No formal statistical testing is planned.

7.5.1. Investigator Electrocardiogram Assessment

A shift table of the investigators' assessment of ECG results at worst outcome during study compared with baseline values will be presented by treatment group using the following categories: normal; abnormal, not clinically significant; abnormal, clinically significant; or

missing. The number and percentage of subjects in each cross-classification group of the shift table will be presented. Subjects with a missing value at baseline or postbaseline will not be included in the denominator for percentage calculation. No formal statistical testing is planned.

A by-subject listing for ECG assessment results will be provided by subject ID number and visit in chronological order.

7.5.2. Corrected QT Intervals

The QT interval (measured in millisecond [msec]) is a measure of the time between the start of the Q wave and the end of the T wave in the heart's electrical cycle. The QT interval represents electrical depolarization and repolarization of the ventricles. The QT interval is affected by heart rate, and a number of methods have been proposed to correct QT for heart rate.

Corrected QT (QTc) intervals will be derived using Fridericia's correction (QTcF) as follows:

$$QTcF = \frac{QT}{\sqrt[3]{RR}}$$

where QT is measured in msec; $RR = 60/\text{Heart Rate}$ (beats per min [bpm]) and RR is measured in seconds

The maximum postdose QTcF interval values obtained during the study will be summarized within the following categories:

- > 450 msec
- > 480 msec
- > 500 msec

The maximum postdose change in QTcF interval values obtained during the study will also be summarized within the following categories:

- > 30 msec
- > 60 msec

7.5.3. PR and QRS Intervals

The PR interval (measured in msec) is a measure of the time between the start of the P wave (the onset of atrial depolarization) and the beginning of the QRS complex (the onset of ventricular depolarization). The QRS interval measures the duration of the QRS complex. The maximum ventricular rate (VR) and PR and QRS intervals observed during the study will be categorized. The number and percentage of subjects having values in the following ranges will be presented by treatment group:

- VR > 100 bpm

- PR interval > 200 msec
- QRS interval > 110 msec

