- History of stroke or intracranial hemorrhage within 12 months of randomization or enrollment; subjects requiring therapeutic anticoagulation for any indication should be discussed with the GCLLSG coordinating physician and/or medical monitor prior to screening
- Legal incapacity, prisoners or subjects institutionalized by regulatory or court order, or any individual in dependence to study sponsor or any investigator
- Use of a strong CYP3A4 or a strong P-gp inducer within 2 weeks of first dose of study treatment or anticipated chronic use while on study
- Demonstration of QTc interval > 450 milliseconds or requirement for ongoing treatment with concomitant medications that prolong the QT interval
- Known hypersensitivity to obinutuzumab, idelalisib, tirabrutinib, or any of the excipients

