5. INVESTIGATIONAL MEDICINAL PRODUCTS

5.1. Randomization

It is the responsibility of the Investigator to ensure that subjects are eligible for the study prior to randomization or enrollment. Subjects will be assigned a unique screening number at the time of consent. A medical review of selected screening data will be performed by members of the GCLLSG to confirm eligibility and must be completed prior to randomization or enrollment.

Once eligibility is confirmed, subjects will be assigned a unique subject number from the interactive web response system (IWRS), randomized in a 1:1 ratio to treatment with the combination of tirabrutinib and idelalisib with and without obinutuzumab. The randomization will be stratified by the presence of del17p/TP53mut in CLL cells. Once a subject number is assigned to a subject, it will not be reassigned to another subject. This is an open-label study.

With Amendment 3, randomization of subjects will no longer be performed as only Arm B of the study will continue to enroll.

All Day 1 tests and procedures must be completed prior to the dispensation and administration of the first dose of study treatment on Week 1 Day 1.

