6.7. End of Treatment

The EOT visit should be scheduled for 30 days following discontinuation of all study treatment to satisfy the requirement for a 30-day post-treatment safety assessment. Please consider enrollment of subjects at EOT in the non-interventional GCLLSG CLL registry for subjects that did not enroll at screening.

For subjects that permanently discontinue all study treatment prior to the Week 25 visit without experiencing disease progression, the Week 25 Day 1 visit should be performed on schedule per the Study Procedures Table ([Appendix 2](#)).

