7.2. Laboratory Evaluations

Laboratory data collected during the study will be analyzed and summarized using both quantitative and qualitative methods. Summaries of laboratory data in [Appendix 9](#) will be provided for the Safety Analysis Set and will include data collected up to the last dose of study drug plus 30 days for subjects who have permanently discontinued study drug. The analysis will be based on values reported in conventional units. When values are below the LOQ, they will be listed as such, and the closest imputed value will be used for the purpose of calculating summary statistics as specified in [Section 3.7](#). Hemolyzed test results will not be included in the analysis, but they will be listed in by-subject laboratory listings.

A by-subject listing for laboratory test results will be provided by subject ID number and visit in chronological order for hematology, serum chemistry, and coagulation, separately. Values falling outside of the relevant reference range and/or having a severity grade of 1 or higher on CTCAE severity grade will be flagged in the data listings, as appropriate.

No formal statistical testing is planned.

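### SAP 7.5.3 counts high ventricular rate, PR and QRS values with no postdose limit and no baseline reference, so stable pre-existing findings cannot be told from new ones

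*SAP*

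**What the plan says.** SAP 7.5.3 sets the rule for three ECG measures: "The maximum ventricular rate (VR) and PR and QRS intervals observed during the study will be categorized". It then says: "The number and percentage of subjects having values in the following ranges will be presented by treatment group". The ranges are VR > 100 bpm, PR > 200 msec and QRS > 110 msec. The section mentions no baseline value, change or shift.

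SAP 7.5.2 handles QTcF differently. For the level: "The maximum postdose QTcF interval values obtained during the study will be summarized within the following categories". For the change, with categories > 30 and > 60 msec: "The maximum postdose change in QTcF interval values obtained during the study will also be summarized within the following categories".

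SAP 7.5.1 plans a shift table from baseline to worst outcome, but of the investigator's overall ECG reading (normal; abnormal, not clinically significant; abnormal, clinically significant), together with a by-subject listing of the assessments.

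On timing, the schedule places an ECG at Screening and another at Week 1 Day 1, and Protocol 5.1 states: "All Day 1 tests and procedures must be completed prior to the dispensation and administration of the first dose". On eligibility, the only ECG measurement that excludes a subject in Protocol 4.3 is "Demonstration of QTc interval > 450 milliseconds".

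**The concern.** There are two separate gaps.

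First, 7.5.3 does not say that the maximum is taken over postdose ECGs only. Because 7.5.2 does say so, a programmer who follows the text word by word could include the Screening and Week 1 Day 1 tracings. A value seen only before treatment would then put a subject in the table.

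Second, and independently of how the first gap is resolved, there is no baseline reference. Subjects with a long PR, a wide QRS or a fast rate at entry are not excluded. If the value persists unchanged, they are counted exactly as a subject who crosses the cut-off on treatment would be.

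What is at stake is whether this one table can be interpreted. With about 6 subjects in Arm A and 30 in Arm B, a few carried-over findings could make up most or all of a cell. SAP 7.1.7 also makes treatment-emergent cardiac arrhythmias an AE of interest, and the term list in SAP Appendix 7 includes PR prolongation, QRS prolongation and sinus tachycardia. That AE table is built on treatment-emergent events and the ECG table is not, so the two would not line up.

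A lesser matter is that the ECG sections set no upper time limit. For subjects who stop all drugs early without progression, Protocol 6.7 says "the Week 25 Day 1 visit should be performed on schedule per the Study Procedures Table", and that visit includes an ECG. By contrast, the laboratory summaries in SAP 7.2 "will include data collected up to the last dose of study drug plus 30 days".

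**Working it through.** The plan states no figure for this table, so there is none to reproduce. The check compares the rules and then adds arithmetic for scale.

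**1. The rules side by side**

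| Measure | Postdose limit | Baseline reference |
|---|---|---|
| QTcF (7.5.2) | yes | change > 30, > 60 msec |
| VR, PR, QRS (7.5.3) | not stated | none |
| Investigator's overall reading (7.5.1) | worst outcome during study, contrasted with baseline | shift table |

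**2. Does a general rule fill the gap?** No. SAP 3.8.2 covers nominal visits and unscheduled visits (for the baseline value and the maximum toxicity grade). SAP 3.8.3 defines baseline and chooses among multiple records. Neither limits a maximum *during the study* to postdose data. SAP 3.8.3 does supply a usable baseline (last nonmissing value on or before the first dosing date), so a baseline comparison is feasible.

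**3. Pre-dose share of the ECGs.** As the row reads in SAP Appendix 1, ECGs fall at Screening, Week 1 Day 1, Weeks 5, 9, 13, 17, 21 and 25, and EOT, which makes 9. Two precede dosing: 2/9 = 22%. The count after Week 25 depends on how the table is laid out; the two pre-dose ECGs do not.

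Suppose isolated readings above a cut-off occur independently with probability q per ECG, with no drug effect and all ECGs done. The chance of being counted is 1 − (1 − q)^9 over all ECGs and 1 − (1 − q)^7 over postdose ECGs:

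| q (assumed) | all 9 | 7 postdose | difference |
|---|---|---|---|
| 1% | 8.6% | 6.8% | 1.8 points |
| 2% | 16.6% | 13.2% | 3.4 points |
| 5% | 37.0% | 30.2% | 6.8 points |

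This is the size of the first gap if pre-dose ECGs are included.

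**4. Carried-over findings.** Let p be the share of subjects above *one given* cut-off at baseline and still above it on at least one postdose ECG. The documents do not give p, so a range is assumed. Arm sizes (about 30 and 6) are from SAP 1.3. Expected count = n × p; chance of at least one = 1 − (1 − p)^n.

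| p (assumed) | Arm B expected (30p) | Arm B, at least one | Arm A, at least one (n = 6) |
|---|---|---|---|
| 2% | 0.6 | 45.5% | 11.4% |
| 5% | 1.5 | 78.5% | 26.5% |
| 10% | 3.0 | 95.8% | 46.9% |
| 20% | 6.0 | 99.9% | 73.8% |

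These counts arise with zero drug effect and remain even if only postdose ECGs are used. They apply to each cut-off separately, because 7.5.3 reports three ranges and no composite.

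**5. Late ECGs.** Week 25 Day 1 is 24 × 7 = 168 days after first dose. A subject who stops almost at once without progression could have an ECG about 24 weeks after the last dose. That is the extreme case, and no frequency can be derived from the documents. EOT is scheduled about 30 days after stopping with a ±7-day window, so an on-schedule EOT ECG can fall up to 30 + 7 = 37 days after the last treatment.

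**The case against.** The strongest reply is that this is a side table and that its wording can be read sensibly. SAP 7.5 says the ECG analyses are meant to find meaningful QT changes and that further analyses may follow if something of interest appears. The protocol's safety endpoint is AEs and SAEs, its synopsis evaluates safety by AEs and laboratory tests, and no comparison between arms is intended. SAP 7.5.3 does not label its counts treatment-emergent. All of this stands, and it limits the importance of the point.

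Two stronger readings are tempting and should not be drawn.

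- A reader might infer that the plan *will* report pre-dose ECGs as on-study findings. No passage instructs that. It is the literal reading, supported by the contrast with 7.5.2, but 7.5.1 uses *during study* in contrast to baseline, and a programmer could carry that sense into 7.5.3. The accurate statement is that pre-dose ECGs may be counted.
- A reader might infer that the trial cannot show any effect on conduction or heart rate. That ignores the 7.5.1 shift table and listing, and the arrhythmia AE summaries, which under SAP 7.1.5.1 cover onset from drug start to 30 days after discontinuation plus AEs leading to discontinuation. These give baseline-referenced and treatment-emergent information, though none of them is a shift of PR, QRS or VR.

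It is also fair to note that the QTcF level categories carry no baseline split. They are, however, paired with change categories, which 7.5.3 lacks. The late-ECG point is bounded by Protocol 3.5, which ends monitoring up to 30 days after treatment, or at Week 25 for early stoppers without progression. It is therefore an optional refinement.

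The missing baseline reference survives all of this, because it does not depend on how *during the study* is read.

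**Conclusion.** The point holds. SAP 7.5.3 omits the postdose limit that 7.5.2 states, and it has no baseline reference. The first omission is an ambiguity to close. The second means that, on any reading, stable pre-existing values above a cut-off are counted and cannot be separated from new ones in that table.

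The size depends on a baseline prevalence that the documents do not give. Under the assumed 2% to 20% per cut-off, Arm B would carry 0.6 to 6 such subjects on average. That figure rests on about 30 subjects in Arm B and on persistence of the baseline finding.

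The effect is limited to a descriptive safety table. It does not reach the primary endpoint, the sample size or the AE summaries. The change is worth making because it is nearly free and alters what the counts mean.

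**What to change.** In SAP 7.5.3, replace the maximum observed during the study with the *maximum postdose* value. For each of VR, PR and QRS separately, present one of the following:

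- a shift of baseline status (at or below the cut-off, above it, missing) against maximum postdose status; or
- the number above the cut-off postdose among subjects at or below it at baseline, with that group as the denominator.

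The baseline definition in SAP 3.8.3 can be used unchanged.

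Optionally, in 7.5.1 to 7.5.3, flag or separate ECGs taken well after the last dose, such as the Week 25 ECG of early stoppers. The limit should keep the scheduled EOT ECG, that is 30 days plus its 7-day window. A strict cut at last dose + 30 days would drop on-schedule EOT tracings from days 31 to 37.

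The cost is a wording change, a filter on ECG data already scheduled for collection, and slightly more table output. If the SAP is already final, SAP Section 1 provides for documenting the change in the CSR.
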